9 STUDY DRUG SUPPLIES, DOSING, AND CONCOMITANT MEDICATIONS

9.1 BSI-045B

BSI-045B injection is manufactured in compliance and supplied by Wuxi, China. The drug substance and drug product are manufactured in compliance with Good Manufacturing Practices. All study drugs sent to the study sites will be labeled according to current Good Clinical Practice (GCP) and local Therapeutic Goods Administration requirements.

The strength is 300 mg/2.5 mL/vial/120 mg/mL. Target filling volume is 3.16 mL.

9.2 Receipt, Dispensing, Storage, and Return of Investigational Product

BSI-045B injection is provided free of charge by the Sponsor. The clinical research site is responsible for the storage, dispensing, and administration of the study drug under recommended conditions according to the approved study protocol. The drugs used in this study will be received, stored, and dispensed by the site pharmacist, and the receipt, administration, distribution, and return of the IP will be documented in accordance with the standard operating procedures of the site. The IP is sensitive to light and high temperatures and should be stored and transported at 2°C to 8°C, protected from light. At the end of the study, the Investigator or designee will return the packaging of all used drugs and the remaining unused drugs to the Sponsor.

9.3 Concomitant Medications

Concomitant medications for AE treatment are allowed during the study.

The use of female contraception medications is allowed.

Oral antibiotics are permitted.

Use of nonprescription eye lubricant drops is permitted.

If it is medically necessary to initiate concomitant medications during the study, they will be recorded on the Case Report Form (CRF) and the Medical Monitor and/or Sponsor might be notified. All medications taken within 30 days of Screening will be recorded on the appropriate CRF.

9.4 Rescue Medications for Exacerbations of Atopic Dermatitis

No rescue medication will be permitted during the study.

9.5 Prohibited Concomitant Medications

The use of any other investigational agent during the study is prohibited.

The following interventions are restricted from Screening through completion of the study:

V4.0_8 Jul 2024 Page 54 of 68

- 1) Treatment with a live (attenuated) vaccine or any investigational drug
- 2) Treatment with topical emollients containing additives such as ceramide, hyaluronic acid, urea, or filaggrin degradation products (patients may continue to use stable doses of such moisturizers if initiated before the initiation of study drug but should not change to a different product during the study).
- 3) Treatment with systemic corticosteroids or nonsteroidal systemic immunosuppressive drugs (eg, cyclosporine, methotrexate, mycophenolate, azathioprine, calcineurin inhibitors, etc.) within 2 weeks prior to and during treatment with the study drug. However, inhaled steroids are allowed.

The following procedures are prohibited during participation in the study:

- 1) Major surgical and major dental procedures
- 2) Phototherapy including facials
- 3) Tanning in a bed/booth
- 4) Bleach baths

9.6 Drug Compliance

During recruitment and the Screening Phase, the purpose of this study will be described in detail to fully inform the patient, along with basic information about the study drug, the protocol, the study procedures, the dosing regimen (eg, dose, route of administration, etc.), clinical observation, frequency and process of biological sample collection, potential risks of participating in the trial, compensation and indemnification, etc. Information included in the ICF will allow the patient to decide whether to participate in the study and will help to increase compliance with the study drug. Before administration of study drug, the patient number and dose of the patient will be checked. After administration, administration instruments will be checked and the remaining study drug and empty packages will be counted.

V4.0_8 Jul 2024 Page 55 of 68

10 ADVERSE EVENT REPORTING

10.1 Definitions, Acquisition, and Recording of Adverse Events

An AE is defined as any untoward medical occurrence in a patient administered study drug and which does not necessarily have a causal relationship with the treatment. An AE can therefore be an unintended sign (including an abnormal laboratory finding), symptom, or disease temporally associated with the use of a study drug, whether or not related to study drug.

10.2 Definition of Serious Adverse Event

An event is considered serious if, in the view of either the Investigator or Sponsor, it results in any of the following outcomes:

- 1) Death
- 2) A life-threatening AE (places the patient at immediate risk of death)
- 3) Inpatient hospitalization or prolongation of existing hospitalization
- 4) A persistent or significant disability/incapacity or
- 5) A congenital anomaly of birth defect
- 6) Other important medical event. Infections resulting from contaminated study drugs will be considered a medically important event and subject to expedited reporting

An SAE may or may not be related to study drug.

10.3 Assessment of Causal Relationship of Adverse Events and Serious Adverse Events

The Investigator must separately determine the relationship of the event to the study drug. The causal association of an AE or SAE to study drug administration should be determined as follows: AEs or SAEs that are considered to have a definite, probable, or possible relationship to treatment with the study drug will be recorded as "related/suspected" while those that are considered to be unlikely or unrelated to treatment with the study drug will be recorded as "unrelated/not suspected".

The causal relationship of an AE or SAE will be classified in two categories, suspected and not-suspected, according to the detailed criteria defined in Section 10.6. It is the responsibility of the Investigator to provide the causality analysis when recording an SAE Report; however, the Sponsor, through the pharmacovigilance service provider (Acumen Medical Information & Technology Co., Ltd., [AMIT]), may provide additional analysis and assessment while submitting the report to FDA following the local regulations.

V4.0_8 Jul 2024 Page 56 of 68

10.4 Assessment of Severity of Adverse Events and Serious Adverse Events

The Investigator must determine the severity of each AE based on the grade in Common Terminology Criteria for Adverse Events (CTCAE)v5.0 (Table 10). Severity describes the intensity of the AE. Events that change severity during the course of follow up should be recorded on separate rows on the CRF, using the appropriate verbatim term but with the start date of each new event corresponding to the date that the severity increased or decreased.

Table 10. Assessment of Severity of an Adverse Event

Grade	Definition
Grade 1	Mild; asymptomatic or mild symptoms; clinical or diagnostic observations
	only; intervention not indicated.
Grade 2	Moderate; minimal, local or noninvasive intervention indicated; limiting age-
	appropriate instrumental ADL*.
Grade 3	Severe or medically significant but not immediately life-threatening;
	hospitalization or prolongation of hospitalization indicated; disabling; limiting
	self-care ADL**
Grade 4	Life-threatening consequences; urgent intervention indicated.
Grade 5	Death related to AE

^{*}Instrumental ADL refer to preparing meals, shopping for groceries or clothes, using the telephone, managing money, etc.

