10.5 Adverse Event and Serious Adverse Event Reporting

The AE reporting period starts with signing the ICF. Any AE collected before the first administration of study drug is considered not suspected or not related to the study drug, therefore will not be counted as a related AE in the final Clinical Study Report. Collection of AEs continues throughout the study.

When an AE/SAE occurs, it is the responsibility of the Investigator to review all documentation (eg, hospital progress notes, laboratory reports, and diagnostic reports) related to the event. The investigator will then record all relevant AE/SAE information in the CRF. The SAE information will be recorded in the SAE Report Form provided by AMIT. It is not acceptable for the Investigator to send photocopies of the patient's medical records to AMIT in lieu of completion of the SAE Report Form/AE/SAE CRF page, unless such medical records are requested by AMIT for further understanding the AE/SAE cases. The Investigator will attempt to establish a diagnosis of the event based on signs, symptoms, and/or other clinical information. Whenever possible, the diagnosis (not the individual signs/symptoms) will be documented as the AE/SAE.

For each AE/SAE, the Investigator must document in the medical record that they have reviewed the AE/SAE and provided an assessment of causality. There may be situations in which an SAE occurs but the Investigator has minimal information to include in the initial report to the Sponsor. However, it is very important that the Investigator always make an assessment of causality for every event before the initial transmission of the SAE data to the

V4.0_8 Jul 2024 Page 57 of 68

^{**}Self-care ADL refer to bathing, dressing and undressing, feeding self, using the toilet, taking medications, and not bedridden.

Sponsor. The Investigator may change their opinion of causality in light of follow-up information and send an SAE follow-up report with the updated causality assessment. The causality assessment is one of the criteria used when determining regulatory reporting requirements.

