11.5 Safety Assessments

All AEs will be coded using the Medical Dictionary for Regulatory Activities. An AE (classified by preferred term) will be considered a TEAE if it was not present before the first dose of study drug or if it was present before the first dose of study drug but increased in severity during the assessment period for AEs. The incidence of TEAEs will be summarized by system organ class and preferred term. Multiple AEs mapped to the same preferred term will be counted once per patient.

Concomitant medications will be coded using The World Health Organization (WHO) Drug Dictionary with generic term and Anatomical Therapeutic Chemical (ATC) code and summarized by ATC code and WHODrug generic name. Safety laboratory findings, AEs, vital signs, and 12-lead ECGs will be summarized using descriptive statistics. Values and changes from baseline at scheduled time points will be summarized. Laboratory data will be listed and values and changes from baseline will be summarized.

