# 4.1.6 Partial/Missing Dates

For partial dates, the algorithms for imputation will vary depending upon the parameter; missing or incomplete medications start and stop dates will be imputed to determine

whether the medications are taking concomitantly. Missing AE start dates will be imputed to determine whether the adverse events are treatment emergent. In listings, all dates will be listed as recorded. The details of imputation rules can be found in Appendix 1.

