#### 4.8.2 Adverse Events

Adverse events will be coded using the MedDRA dictionary version 27.0 or higher. The severity of the toxicities will be graded according to the NCI CTCAE version 5.0.

Treatment emergent adverse events (TEAEs) are defined as AEs that started or worsened in severity on or after the first dose of study drug.

TEAEs will be summarized by system organ class (SOC) and preferred term (PT) in descending order of frequency. For each TEAE, the percentage of participants who experience at least 1 occurrence of given event will be summarized.

Causal relationship and toxicity grade are required entries on the adverse events eCRF, so missing data are not expected. However, any AEs with missing causal relationships will be imputed as 'Related' and any missing toxicity grades will be imputed to grade 3 for summary but still keep missing in listing.

A subject with more than one occurrence of the same adverse event in a particular system organ class will be counted only once in the total of those experiencing adverse events in that particular system organ class. If a subject experience the same adverse event at more than one severity, or with more than one relationship to study drug, the most severe rating or the stronger causal relationship to study drug will be given precedence.

The numbers of subjects and incidence rate for all TEAEs, TEAEs of BSI-045B-related for following category will be tabulated:

- 1) Overview of TEAEs
- 2) TEAEs by SOC and PT
- 3) TEAEs by SOC and PT and by Maximum NCI CTCAE grade
- 4) Serious TEAEs by SOC and PT
- 5) Grade>=3 TEAEs by SOC and PT
- TEAEs Leading to BSI-045B Interruption by SOC and PT

7) TEAEs Leading to BSI-045B Withdrawn by SOC and PT

8) TEAEs Leading to Death by SOC and PT

The following AE listings of all subjects will be provided.

- 1) All AEs
- 2) BSI-045B Related AEs
- 3) Serious AEs
- 4) AEs Leading to BSI-045B Withdrawn
- 5) AEs Leading to Death

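### Because each severity change opens a new dated CRF row, SAP 4.8.2 can flag a pre-dose adverse event that only improved as treatment-emergent, which Protocol 11.5 would not do

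*Protocol*

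**What the plan says.** **Recording.** Protocol 10.4: "Events that change severity during the course of follow up should be recorded on separate rows on the CRF", and each such row is dated "with the start date of each new event corresponding to the date that the severity increased or decreased". Decreases are named explicitly, and the row is called a new event. Protocol 10.5: "The AE reporting period starts with signing the ICF". An event can therefore have a row from before first dose and another from after it.

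**SAP definition.** SAP 4.8.2: "Treatment emergent adverse events (TEAEs) are defined as AEs that started or worsened in severity on or after the first dose of study drug". SAP 4.1.6: "Missing AE start dates will be imputed to determine whether the adverse events are treatment emergent". Appendix 1 fills in a missing AE start date solely to set this flag. For a subject with the same event at several grades or with several causality ratings, SAP 4.8.2 adds that "the most severe rating or the stronger causal relationship to study drug will be given precedence".

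**Protocol definition.** Protocol 11.5 classifies by preferred term. An event counts "if it was not present before the first dose of study drug", or if it was already there and its severity then rose.

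**The concern.** The recording rule and the SAP definition were written separately and do not fit together. A row opened because an event got better has a start date after first dose, and starting after first dose is enough to meet the SAP definition. An improvement can therefore be tabulated as an event that emerged on treatment.

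The incidence of adverse events is part of the primary safety endpoint. The trial has one arm and no blinding, so the comparison with each patient's own pre-dose state is the main basis for calling an event emergent. No control group would show the same artefact. The Grade 3 or higher table is exposed too: a pre-dose event that falls from Grade 4 to Grade 3 after dosing would enter it. Protocol and SAP would then give different counts for the same patients.

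**Working it through.** The plan states no figure on this point, so there is none to reproduce. The check applies the definitions to example events. First dose is Day 1, as in SAP 4.1.3.

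- **SAP by row:** TEAE if any row starts on or after Day 1. A worsening opens its own row, so the second limb of the definition adds nothing here.
- **SAP by episode:** all rows of one event are treated as a single AE with its first onset date.
- **Protocol 11.5:** TEAE if the preferred term has a post-dose row and either no pre-dose row or a post-dose grade above the pre-dose grade.

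| Event | SAP by row | SAP by episode | Protocol 11.5 |
|---|---|---|---|
| Grade 2 on Day -5, Grade 1 on Day 10 | TEAE | no | no |
| Grade 1 on Day -5, Grade 2 on Day 10 | TEAE | TEAE | TEAE |
| Grade 2 on Day -5, unchanged | no | no | no |
| Grade 1, first seen on Day 10 | TEAE | TEAE | TEAE |
| Grade 2 on Day -5, Grade 1 on Day 10, Grade 2 on Day 20 | TEAE | depends on the reference grade | no, against the pre-dose grade |
| Resolved before Day 1, recurs later at the same grade | TEAE | TEAE | no, if read literally |

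**Direction.** Any event that Protocol 11.5 counts is either new after first dose or has increased after it. Either way it has a row dated after first dose, so the row reading counts it as well. The reverse fails in the first, fifth and last lines. Relative to Protocol 11.5, the row reading can only add events.

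**Size.** One extra patient in a table cell adds 100 × 1/N percentage points, where N is the size of the Safety Analysis Set.

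- N = 20: 100 × 1/20 = 5.0 points.
- N = 24: 100 × 1/24 = 4.2 points.

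The values 20 and 24 are the planned numbers of evaluable patients. SAP 3 puts everyone who received at least one dose in the Safety Analysis Set, and Protocol 7.3 replaces patients who do not complete the first 5 doses. N can therefore exceed 24, which makes the step smaller. The step is zero if the patient already has a genuine TEAE in the same cell.

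**Frequency.** The sequence needs an event that starts after consent, is still present at first dose at Grade 2 or higher, and then steps down. A Grade 1 event that resolves has no lower grade to open a row for. The documents give no rate for this sequence.

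**The case against.** The strongest reply is that SAP 4.8.2 means the whole event, not the CRF row. If every row were an AE, the words about worsening would be redundant, because each worsening already opens its own row. The same section also speaks of one adverse event occurring at more than one severity. On this reading an event that only improves neither began nor worsened after dosing, and SAP and protocol agree on it. This reading is open, so a reader who infers that the SAP is plainly wrong as written goes too far.

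It does not remove the problem. Protocol 10.4 calls the row a new event and gives it its own start date, and the SAP sets the flag from start dates. It provides no original-onset date and no rule for joining rows; whether the eCRF links them cannot be seen from the documents. The precedence rule governs which grade or causality is shown for a subject, and does not compare with the pre-dose grade.

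Three other inferences are tempting, and the documents do not support them.

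- **That such events are likely because washout can last 12 weeks.** Protocol 7.2 sets 12 weeks only for tralokinumab and dupilumab. Topical corticosteroids and calcineurin inhibitors need 1 week, and patients without washout have up to 2 weeks of screening. The number of patients needing a long washout is not given.
- **That every such patient raises the overall TEAE rate by 4.2 to 5.0 points.** In Phase 1, most or all healthy volunteers in each cohort had at least one TEAE, although only 2 of 5 patients with atopic dermatitis did. A patient with another TEAE does not move the overall rate.
- **That improvement is turned into drug toxicity.** Related TEAEs are tabulated separately, and Protocol 10.5 treats events collected before first dose as unrelated. Whether that covers a row opened after dosing is not clear, but it weakens the inference. The listing of all AEs also keeps the pre-dose row visible.

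**Conclusion.** The point stands as a gap in the SAP. If SAP 4.8.2 is applied to the rows that Protocol 10.4 tells sites to record, a pre-dose event that only improves after dosing is counted as a TEAE, and Protocol 11.5 does not count it. This rests on the flag being programmed from recorded start dates, which the SAP's own date rules suggest but do not compel.

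The bias is upward only. It is 5.0 points per patient in a cell at N = 20 and 4.2 at N = 24, less if replacements enlarge the Safety Analysis Set, and nothing where the cell already holds a genuine TEAE. The number of patients affected is unknown and may be zero. The analysis is descriptive, so no test is affected. The change is still worth making, because it concerns a primary safety endpoint and needs no new data.

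**What to change.** In SAP 4.8.2, adopt the Protocol 11.5 definition and write it for the rows as collected:

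- A post-dose row is a TEAE only if the same preferred term was not present before first dose, or if the row's grade exceeds the pre-dose grade of that term.
- A row opened by a decrease in the severity of a pre-dose event is never a TEAE on that basis.
- State whether the reference is the worst or the last pre-dose grade. Protocol 11.5 does not say, and it matters: for a term that goes from Grade 2 to Grade 1 before dosing and back to Grade 2 afterwards, the last grade gives a TEAE (2 > 1) and the worst grade does not (2 is not above 2).
- State how a preferred term that resolved before dosing and recurs afterwards is classified. If an episode rule is preferred for this case, amend Protocol 11.5 to match, so that both documents give the same count.

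SAP 4.8.9 uses the same kind of definition for treatment-emergent conjunctivitis; align it where conjunctivitis is taken from AE rows.

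The cost is one SAP paragraph and some programming, plus a protocol wording change only if the episode rule is chosen.

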10.5 Adverse Event and Serious Adverse Event Reporting

The AE reporting period starts with signing the ICF. Any AE collected before the first administration of study drug is considered not suspected or not related to the study drug, therefore will not be counted as a related AE in the final Clinical Study Report. Collection of AEs continues throughout the study.

When an AE/SAE occurs, it is the responsibility of the Investigator to review all documentation (eg, hospital progress notes, laboratory reports, and diagnostic reports) related to the event. The investigator will then record all relevant AE/SAE information in the CRF. The SAE information will be recorded in the SAE Report Form provided by AMIT. It is not acceptable for the Investigator to send photocopies of the patient's medical records to AMIT in lieu of completion of the SAE Report Form/AE/SAE CRF page, unless such medical records are requested by AMIT for further understanding the AE/SAE cases. The Investigator will attempt to establish a diagnosis of the event based on signs, symptoms, and/or other clinical information. Whenever possible, the diagnosis (not the individual signs/symptoms) will be documented as the AE/SAE.

For each AE/SAE, the Investigator must document in the medical record that they have reviewed the AE/SAE and provided an assessment of causality. There may be situations in which an SAE occurs but the Investigator has minimal information to include in the initial report to the Sponsor. However, it is very important that the Investigator always make an assessment of causality for every event before the initial transmission of the SAE data to the

V4.0_8 Jul 2024 Page 57 of 68

^{**}Self-care ADL refer to bathing, dressing and undressing, feeding self, using the toilet, taking medications, and not bedridden.

Sponsor. The Investigator may change their opinion of causality in light of follow-up information and send an SAE follow-up report with the updated causality assessment. The causality assessment is one of the criteria used when determining regulatory reporting requirements.

An AE or SAE is considered "unexpected" if it is not listed in the BSI-045B Investigator's Brochure or is not listed at the specificity or severity that has been observed. "Unexpected" as used in this definition also refers to AEs, SAEs, or suspected adverse reactions that are mentioned in the IB as occurring with a class of drugs or as anticipated from the pharmacological properties of the drug, but are not specifically mentioned as occurring with the particular drug under investigation.

Patients in this study who experience an AE or SAE will be followed until the AE or SAE is resolved, has stabilized and is not expected to change, or is clearly determined to be due to a patient's stable or chronic condition or intercurrent illness, even if this occurs after the Termination Visit. All AEs spontaneously reported by the patient and/or in response to an open question from study personnel or revealed by observation, physical examination, or other diagnostic procedures will be recorded and reported on the appropriate CRF.

When a unifying diagnosis has been made that accounts for several possible signs and/or symptoms, the unifying diagnosis should be selected as the AE term. For example, the combination of general malaise, mild fever, headache, and rhinitis should be described as "upper respiratory syndrome" if this diagnosis has been made, rather than reporting the individual symptoms as separate events.

Safety and tolerability will be determined by symptoms, signs, and laboratory test abnormalities. The Investigator will monitor the laboratory test findings. If any laboratory test is abnormal during the course of the study, it will be followed at the discretion of the Investigator. Abnormalities of laboratory tests, in the opinion of the Investigator, may be considered of potential clinical concern and, thus, constitute a laboratory AE or be associated with a clinical AE. In such cases, they must be reported on the AE Form.

